## **The SPENCER Study**

---

Accurate records of all trial material used by study site (e.g., dates, subject number, kits used, kits unused, etc.) should be maintained and recorded. A study team member will periodically check the supplies of trial material held at the site to verify accountability of all trial material. The Investigator must keep an accurate accounting of trial material received from the supplier by maintaining a detailed inventory. This includes the amount of trial material received by the site, amount used, the amount destroyed by the site, and the amount returned to the Sponsor or designee (as applicable) upon completion of the trial. All trial material that is used during the trial must be accounted for on a drug accountability form, or equivalent.

The trial material must not be used outside of this clinical trial. The Investigator or site personnel may not supply the trial material to other sites, Investigators, or subjects, or allow the trial material to be used other than as directed by this protocol without prior authorization from Ocular Therapeutix, Inc.

## **7 SELECTION AND WITHDRAWAL OF SUBJECT**

There will be up to 80 eyes enrolled in this study.

### **7.1 Inclusion Criteria**

Subjects will be eligible for study participation if they:

1. Are planning to undergo non-complicated CCI CE/PCIOL in one or both eyes with or without iStent/Hydrus/Goniotomy.
2. Are willing and able to comply with clinic visits and study related procedures
3. Are willing and able to sign the informed consent form

### **7.3 Subject Recruitment and Screening**

Each subject that is screened will be assigned a subject identification (ID) consisting of a 2-digit site number plus a 2-digit subject number. The subject ID will be used as the primary subject identifier for the duration of the study. For example, Site 01 with the first subject would be 01-01.

The subject must sign the informed consent form (ICF) before his or her participation in the study. A copy of the ICF must be provided to the subject or the subject's legal guardian. The original signed ICF for each participating subject shall be filed with records kept by the Investigator and must be available for verification by study team members at any time, and a copy will be given to each subject.

### **7.4 Withdrawal Criteria**

Subjects may withdraw from the clinical study at any time for any reason without jeopardy or prejudice and without compromising their clinical care by the Investigator. The Investigator also has the right to withdraw subjects from the trial in the event of an intercurrent illness, adverse event (AE), protocol deviation, and/or administrative reason.

If withdrawal occurs after insertion of DEXTENZA, but before all evaluations are completed, efforts should be made to complete the evaluations, and report the observations up to the time of withdrawal as thoroughly as possible. A complete final evaluation should be performed at the time of the subject's withdrawal with an explanation for the withdrawal. The reason for and date of the withdrawal must be recorded on the subject's case report form (CRF). If the reason for withdrawal is an AE, the AE should be monitored at the discretion of the Investigator (e.g., until the event is resolved or stabilized, the subject was referred to the care of a health care professional, or a determination of a cause unrelated to the trial material or insertion procedure). The specific event(s) or test result(s) are to be recorded in the CRF.

At least 3 documented attempts will be made to contact subjects who are non-compliant or lost to follow-up and such attempts will be documented in the subject's study record.

#### **7.4.1 Withdrawal Methods**

Ocular Therapeutix may terminate this study at any time if safety concerns arise. Reasons for termination may include but are not limited to, the following:

- The incidence or severity of AE in this or other studies point to a potential health hazard for trial subjects
- Any information becoming available during the study that substantially changes the expected benefit risk profile of the study product

#### **7.4.2 Collection of Data from Withdrawn Subjects**

In the event that study discontinuation of a subject is necessary, the Investigator should make every attempt to have the subject complete the Early Termination Visit assessments outlined in Appendix A as soon as possible. The reason for premature discontinuation should be recorded in the subject chart and entered in the CRF.

#### **7.4.3 Subject Replacement**

Subjects who withdraw from the study after having DEXTENZA inserted will not be replaced.

## **8 SUBJECT TREATMENT**

[figure not shown]
### Appendix 3    VAS for Eye Dryness

The following procedures should be followed for conducting the study assessments. The Visual Analog Scale (VAS) should be performed prior to all other ocular assessments.

To complete the VAS questionnaire, ask the subject to rate the severity and the frequency of symptom of eye dryness (0%-100%) by placing a vertical mark (|) on the horizontal line to indicate the level of eye discomfort that they are experiencing in both eyes currently (i.e., right now) and how often the eye dryness is experienced.

0% corresponds to: "no discomfort"

100% corresponds to: "maximal (the most) discomfort"

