## **The SPENCER Study**

---

- Number of attempts to successfully insert Dextenza
- Dry eye severity as measured by VAS at baseline, Day 8 and Day 30
- Record insert retention up to 30 days

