### **8.4.4 Post-Operative Day 8 (Visit 4, Day 8) Day 14 (Visit 5, Day 14) and Day 30 (Visit 6, Day 30)**

At the Day 8, Day 14 and Day 30 Visits, the following assessments will be performed:

- Prior and concomitant medication
- AEs (record incidence and severity of any adverse events that occur after the insertion)
- Distance visual acuity (VA)
- Best-Corrected Visual Acuity
- Ocular pain assessment (0 to 10)
- Slit lamp examination (including anterior chamber count and anterior chamber flare)
- Intraocular pressure
- Insert visualization

- MAC OCT Day 30
- Dry eye severity as measured by VAS on Day 8 and Day 30

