## 10.7 Secondary Efficacy Analysis

Secondary Efficacy Endpoints are

- Mean change in BCVA from Baseline
- Number and percentage of subjects with complete absence of pain
- Number and percentage of subjects with complete absence of cell
- Measuring cell, pain, and flare on Day 8,14,30
- Physician ease of insertion and visualization
- Number of attempts to successfully insert Dextenza
- Dry eye severity as measured by VAS at baseline, Day 8 and Day 30
- Record insert retention up to 30 days

Mean change in BCVA from baseline will be summarized using descriptive statistics (n, mean, standard deviation, median, minimum, and maximum).

The number and percentage of subjects with complete absence of pain and with complete absence of cell will be summarized.

The number and percentage of investigators' responses to ease of insertion and visualization (easier, the same, and more difficult) will be summarized.

The number of attempts to successfully insert DEXTENZA will be summarized.

Dry eye severity as measured by VAS will be summarized using descriptive statistics (n, mean, standard deviation, median, minimum, and maximum).

Insert retention as measured by yes or no will be summarized.

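### As worded, the Appendix 3 VAS does not isolate dry eye severity: it mixes severity with frequency, anchors both on discomfort, and rates the two eyes together

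*Combined protocol and SAP*

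**What the plan says.** The secondary endpoint, in the Synopsis and in Sections 6.2.1.1 and 10.7, is "Dry eye severity as measured by VAS at baseline, Day 8 and Day 30". Frequency of dryness is not named as an endpoint anywhere. Section 8.4.1 schedules the VAS at the pre-operative baseline visit, and Section 8.4.4 repeats it after surgery: "Dry eye severity as measured by VAS on Day 8 and Day 30". Section 10.7 treats it as one quantity: "Dry eye severity as measured by VAS will be summarized using descriptive statistics".

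Appendix 3 says how the score is obtained. The subject is to "rate the severity and the frequency of symptom of eye dryness (0%-100%) by placing a vertical mark" on a horizontal line. The mark is placed "to indicate the level of eye discomfort that they are experiencing in both eyes currently (i.e., right now"). The same sentence then adds a second request, for frequency: "and how often the eye dryness is experienced". Two anchors are given. The lower is "0% corresponds to: 'no discomfort" and the upper is "100% corresponds to: 'maximal (the most) discomfort". The VAS comes before the other ocular assessments. Ocular pain is scored separately, 0 to 10, at the same visits.

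**The concern.** A mean labelled dry eye severity is interpretable only if the number behind it is a severity rating of dryness in the eye under study. Appendix 3 departs from this in three ways. It asks about two constructs and does not say which one the score represents. It anchors the response on a broader sensation than dryness. It also asks about the pair of eyes rather than the study eye.

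The second departure matters most after surgery. Baseline is taken before the operation. Day 8 and Day 30 follow both cataract surgery and the placement of an insert in a punctum. Section 4.3.2 lists eye pain and discomfort among the expected effects of the insertion procedure, and ocular discomfort among the common risks. A scale that runs from no discomfort to maximal discomfort can register these. A reader who compares Day 8 with baseline could then take a rise as worsening dry eye when part of it is something else.

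**Working it through.** The documents state no figure that depends on the VAS. They give no assumed mean, standard deviation or difference, Section 10.2 reports no sample size calculation, and Section 10.3 plans no formal testing. There is nothing to reproduce, so the check compares the endpoint with the instruction that generates it.

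| Feature | Endpoint and analysis (6.2.1.1, 10.7) | Instruction (Appendix 3) |
|---|---|---|
| Construct | Severity | Severity and frequency |
| Symptom | Dry eye | Dryness in the request, discomfort in the description of the mark and in both anchors |
| Time frame | Visit (baseline, Day 8, Day 30) | Present moment for severity; how often, with no recall period, for frequency |
| Unit | Enrolment counted in eyes (4.5, 7) | Both eyes together |
| Number of responses | One quantity summarised | One mark on one line, as far as the wording shows |

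1. *Construct.* A frequency cannot be rated for a single moment, so the instruction cannot be followed literally with one mark. Subjects must choose what to answer, and no scoring rule says how to read the choice.

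2. *Anchors.* Neither end of the line names dryness, and neither can express how often something happens. This holds whether the form has one line or two. On a two-line form the stated anchors would still not fit the frequency line and would still mislabel the severity line, and Section 10.7 would still rely only on the word severity to identify the endpoint.

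3. *Eye.* Section 7.1 admits subjects having surgery in one or both eyes. With one operated eye, a rating of both eyes blends the treated eye with the untreated one. With two, a single number has to serve both.

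4. *Where the effect falls.* Under Section 6.3 all subjects receive the insert and are randomised only to its site. All have cataract surgery and complete the same form. Discomfort from surgery and ambiguity in the wording are therefore expected to be similar in the two groups. They act on the level of the score and on its change from baseline, and they add variability to the comparison of puncta. They would bias that comparison only if insertion-related discomfort differs by site, which the documents do not show.

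**The case against.** The strongest reply is that the questionnaire itself is not available. Appendix 3 gives instructions for completing it, a figure just before it is not shown, and the singular mark could describe how to answer each of two items. This stands as a limit: a two-line form cannot be excluded, so the single-mark reading is conditional. It does not rescue the anchors, as step 2 shows. Similarly, Section 8.4.1 says that baseline ocular assessments are done in each eye, so a per-eye rating may have been intended. Appendix 3 does not ask for one.

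Several stronger readings are tempting and are not supported:

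- *That the scale does not measure dry eye severity at all.* The appendix is titled for eye dryness and the request names that symptom. Dryness severity is in the score, but it is not isolated.
- *That change to Day 8 would largely track surgical discomfort.* The documents do not quantify discomfort at Day 8 or its relation to the VAS. Because pain is recorded at the same visits, a reader could at least see whether the two move together.
- *That a difference between puncta would be uninterpretable or biased.* The surgery and the form are common to both randomised groups, so the main consequence is noise.
- *That the distortion can be put in points.* If 20% to 40% of subjects marked frequency, and frequency differed from severity by 20 points, an arm's mean would move by 0.2 × 20 = 4 to 0.4 × 20 = 8 points. Both inputs are invented. The same expected shift would apply to both arms, leaving the expected contrast unchanged.

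It is also fair to say that this is one of eight secondary endpoints, summarised descriptively, with no decision resting on it. That limits the priority. It does not remove the need for a reported mean to have a defined meaning.

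**Conclusion.** The point holds in a limited form. Following Appendix 3 as written gives a score that mixes dryness severity with frequency and general discomfort, and that is not specific to the study eye. Day 8 and Day 30 values, and their change from baseline, may partly reflect post-operative or insertion discomfort, or the untreated eye. The effect on upper versus lower punctum is mainly added noise. Its size cannot be derived from the documents.

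The conclusion rests on the wording of Appendix 3, since the form was not available. That discomfort enters the post-operative score is a reasonable inference from the anchors and the risks in Section 4.3.2; the plan does not state it. This is a cheap improvement to a descriptive secondary endpoint and does not threaten the primary objectives.

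**What to change.** Reword Appendix 3 and the form as follows:

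- Anchor the severity line at *no dryness* and *worst dryness*, and ask about the study eye.
- If frequency is kept, give it a separate line anchored at *never* and *all of the time*, with a stated recall period.
- In Section 10.7, name the severity line as the endpoint.

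If the form already has two lines, only the anchors, the eye being rated and the naming of the endpoint line need correcting.

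The cost is one reworded form and one sentence in Section 10.7. The downside is that values will be less directly comparable with other uses of the current wording.

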## 8.1 Treatment Regimen

The DEXTENZA insert will be administered, which is designed to be retained in the canaliculus where it provides sustained release of dexamethasone for approximately 30 days.

## 8.2 Prior and Concomitant Therapy

At the discretion of their physician, subjects may continue to receive all medications and standard treatments administered for other conditions. All medications will be collected, including those administered during the insertion procedure.

## 8.3 Product Quality Complaints

All product quality complaints should be reported to Ocular Therapeutix, by email to [[contact]](mailto:[contact]), or by [contact], within 24 hours.

## 8.4 Study Assessment by Visit

### 8.4.1 Screening/Baseline Visit (Visit 1, Day -21 to -1)

At the Screening/Insertion Visit (Visit 1, Day -1), the following assessments will be performed. Ocular assessments will be performed in each eye:

- Informed consent
- Inclusion/exclusion criteria
- Demographics
- Medical and ocular history
- Prior and concomitant medications (record any medication that subject is taking as well as those taken in the previous 60 days)
- AEs (record incidence and severity of any adverse events that occur after the insertion)
- Distance VA
- Best-Corrected Visual Acuity
- Ocular pain assessment (0-10)
- Slit Lamp Examination (including anterior chamber cell count, and anterior chamber cell flare)
- Punctum examination (size and presence of any punctal plug)
- Grade cataract density (scale 1 to 4)
- Intraocular pressure
- Dilated fundus exam
- IOL measurement
- MAC OCT
- Dry eye severity as measured by VAS

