### 4.3.2 Risks

The following adverse reactions are typical adverse events that are known to be expected with the insertion procedure using a standard dilator and blunt, non-toothed forceps: eye pain and discomfort, tearing or epiphora (with or without mucopurulent discharge), eye inflammation, allergic reaction, dacrocystitis, canaliculitis, decreased/impaired visual acuity, stenosis (narrowing/closing of the punctum and/or canaliculus), perforation of or trauma to the punctum and/or surrounding tissues, inability to remove test article, need for surgery on the lacrimal system, infection or intraocular infection that if severe could lead to temporary or permanent impairment of eye sight.

Additionally, based on several decades of use of topical ocular corticosteroids, risks have been identified with the use of dexamethasone, some of which have been observed in clinical trials with the DEXTENZA 0.4 mg dexamethasone insert. The following AEs and/or risks have been observed with the administration of corticosteroids: IOP increase/glaucoma/ocular hypertension, masking of infection or enhancing existing infections, delayed healing, cataracts. Other common risks (occurring in  $\geq 1\%$  of safety population) included anterior chamber inflammation, iritis, visual acuity reduced, corneal oedema, cystoid macular oedema, conjunctival hyperemia, eye pain, ocular discomfort, posterior capsule opacification, intraocular pressure increased, and corneal abrasion.

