## **5 TRIAL OBJECTIVES**

The study objectives are to evaluate the safety and effectiveness of treatment with an intracanalicular dexamethasone (0.4mg) insert in the operating room following cataract surgery/intraocular lens implant (IOL) with or without iStent/Hydrus/Goniotomy when placed in the lower punctum compared to the upper punctum.

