### **6.2.2 Safety Endpoints**

- Adverse events (AEs)
- Intraocular pressure (IOP)

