## 9 ADVERSE EVENTS

The Investigator and study staff are responsible for detecting and recording AEs and serious adverse events (SAEs), during scheduled safety evaluations and whenever such information is brought to their attention.

This section of the protocol provides definitions and detailed procedures to be followed.

During each visit, the Investigator will question the subject about AEs using an open question, taking care not to influence the subject's answers. Throughout the course of the study, every effort must be made to remain alert to possible AEs. If an AE occurs, the first concern should be for the safety of the subject. If necessary, appropriate medical intervention should be provided. At the signing of the ICF, each subject must be given the names and telephone numbers of study site staff for reporting AEs and medical emergencies.

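### No standardized examination of the treated punctum is scheduled after insertion, although the objective is to compare safety between the lower and the upper punctum

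*Combined protocol and SAP*

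**What the plan says.** Section 5 gives the objective as safety and effectiveness of the insert "when placed in the lower punctum compared to the upper punctum". Under Section 6.3 every subject receives the same product, open label, and the only randomized difference is the punctum used.

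Section 4.3.2 lists events expected with the insertion procedure. They include canaliculitis, tearing, and "stenosis (narrowing/closing of the punctum and/or canaliculus), perforation of or trauma to the punctum and/or surrounding tissues".

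The safety endpoints in Section 6.2.2 are AEs and intraocular pressure (IOP). Section 8.4.1 places "Punctum examination (size and presence of any punctal plug" at Visit 1, before insertion, and Appendix 1 marks that row once, in the Visit 1 column. Sections 8.4.2 to 8.4.4 do not list it.

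On AEs, Section 9 makes the investigator and staff responsible for detecting events as well as recording them. At each visit "the Investigator will question the subject about AEs using an open question, taking care not to influence the subject's answers". Section 10.8.1 tabulates AEs by MedDRA class and term, with ocular and non-ocular events apart, and mentions no split by punctum. The synopsis says data will be shown overall where applicable.

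**The concern.** Drug, dose and surgery type are common to both groups, so IOP and most general AEs would be expected to reflect what the groups share. Local effects on the punctum and canaliculus are a plausible place for the groups to differ. That is a statistical reviewer's inference: Section 4.3.2 describes the insertion procedure in general and says nothing about lower versus upper.

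If local findings are noted only when someone happens to see them or the subject complains, mild or symptomless changes such as narrowing can be missed in either group. A safety table with no punctal events would then be hard to interpret, because it could mean that none occurred or that none was looked for. Section 4.3.3 relies on the study visits for prospective diagnosis of complications, but the visit lists contain no item aimed at this one. Even the events that are recorded need not be shown by group.

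**Working it through.** The plan gives no sample size calculation (Section 10.2) and no punctal event rate, so there is no figure to reproduce. The check compares the visit lists, then adds a calculation for scale.

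**Step 1: what each visit can show about the punctum (Sections 8.4.1 to 8.4.4, Appendix 1)**

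| Visit | Punctum examination | Other routes to a local finding |
|---|---|---|
| Visit 1, before insertion | Yes: size, plug | Slit lamp |
| Day 0 | No | AEs, insert visualization, number of attempts, ease of insertion |
| Day 1 | No | AEs, slit lamp, insert visualization |
| Days 8, 14, 30 | No | AEs, slit lamp, insert visualization |
| Early Termination | No | AEs, slit lamp; Appendix 1 also refers these subjects to the final-visit assessments |

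The columns of Appendix 1 are partly broken in the available text, but its single Visit 1 entry agrees with the intact visit lists.

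**Step 2: what the other routes are specified to record**

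- Slit lamp after insertion: the named items are anterior chamber cells and flare.
- Insert visualization: retention is summarized as yes or no (Section 10.7). Whether an insert is visible does not describe the condition of the punctum.
- AEs: any sign or symptom qualifies (Section 9.1), so a punctal finding can be entered, but nothing directs the examiner to look for one.

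Baseline punctum size therefore has no scheduled follow-up value. It may have been intended for eligibility only, since exclusion 10 concerns punctal occlusion.

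**Step 3: scale**

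The synopsis gives 60 to 80 eyes, with up to 40 per group. An equal split, which is an assumption at the 60-eye minimum, gives n = 30 to 40 per group. With zero events among n independent eyes, all fully examined, the one-sided 95% upper bound is 1 − 0.05^(1/n):

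- n = 40: 1 − 0.05^(1/40) = 0.072, or 7.2%
- n = 30: 1 − 0.05^(1/30) = 0.095, or 9.5%

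The chance of recording at least one event in a group is 1 − (1 − p·s)^n, where p is the true rate and s the share detected. Both are assumed:

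| p | s | n = 30 | n = 40 |
|---|---|---|---|
| 1% | 1 | 26% | 33% |
| 2% | 1 | 45% | 55% |
| 5% | 1 | 79% | 87% |
| 10% | 1 | 96% | 98% |
| 5% | 0.5 | 53% | 64% |

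At an assumed 5% rate, missing half the findings lowers the chance of seeing any in 40 eyes from 87% to 64%. The bounds above hold only when s = 1.

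**The case against.** A reader might infer that local harm has no planned measurement after insertion, or that its detection depends on what subjects volunteer. The documents support neither reading. AEs with severity are recorded at every visit from Day 0 to Day 30, the slit lamp is used on Days 1, 8, 14 and 30, and insert visualization directs attention to the treated site at each visit. Section 9 requires staff to detect events, so the open question is one route among several.

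Much of the Section 4.3.2 list would also surface without a special examination. Perforation or trauma from insertion would occur in the operator's presence on Day 0, and the subject can report tearing. What remains is chiefly mild or symptomless change, for which the documents give no rate or time course. The lists of common reactions in Sections 4.1 and 4.3.2 name no punctal event, so a low rate is possible.

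The study is descriptive, with no formal testing (Sections 10.1 and 10.3). A bound on the rate in one group is not a bound on the difference between groups, and both eyes of a subject may enter, so eyes need not be independent.

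These points limit the size of the concern, but they do not supply a structured local outcome or a table by group. The separate SAP mentioned in Section 10.1, the insertion instructions and the Section 8 figure could not be checked. An SAP could add the split by group, but it cannot analyse findings the visits do not collect.

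**Conclusion.** The point holds in limited form. On the available text, the named punctum examination is done once, before insertion, and no later visit requires a standardized look at the treated punctum. Local harm is captured by general AE recording and incidental findings, and no tabulation by punctum group is stated. For a safety comparison between puncta, an absence of reported local events would be weak evidence about mild or symptomless findings.

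The 7.2% to 9.5% bound only indicates scale and rests on the assumptions in the working. It would be wrong to conclude that the trial cannot detect punctal harm, or that it will report equal safety: the plan provides several routes to detection and promises no such conclusion. This is a cheap, worthwhile improvement and does not invalidate the trial.

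**What to change.** - **Visits.** Add a short structured examination of the treated punctum to the slit lamp and insert visualization steps already scheduled. The minimum is Day 30 and Early Termination. Day 1 and Day 8 are preferable as well, because a finding that resolves early would be missed at Day 30.
- **Content.** Record punctum size by the same method as at baseline, and state that method in Section 8.4.1. Record trauma, stenosis and inflammation, each as present or absent. The insert may still be in place around Day 30 (Sections 6.4 and 8.1), so size should be read alongside that visit's visualization result.
- **Text.** Amend Sections 8.4.3 and 8.4.4 and the matching columns of Appendix 1.
- **Analysis.** In Section 10.8, report the number and percentage of eyes with each finding, the change in punctum size from baseline, and ocular AEs, all by assigned punctum.

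The cost is a few CRF items per visit, with no new visit, staff or equipment. Some additional mild findings will be recorded. The examiner remains unmasked, so the change improves completeness of detection but does not remove observer bias.
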